- 1. Sociodemographic: a brief baseline survey will be administered to collect a minimal amount of information. Additional study relevant information (only for enrolled patients) will be collected to enable study analyses.
- 2. Laboratory assessments and other clinical assessments: patients will only be monitored according to their physicians' standard practice without additional study-specified interventions and evaluations. Only available assessments will be collected from routine testing/evaluations using electronic approaches.
- 3. Assessments may not be conducted at the exact scheduled time intervals as there will be no intervention for patients' clinical care. Only available assessments will be collected from routine testing/evaluations. The schedule is to remind physicians to collect data regularly.
- 4. Adverse event and pregnancy exposure reporting: only spontaneous AEs/SAEs and pregnancy exposure related to any GSK products will be reported and summarized.
- 5. The baseline assessment filling with grey colure is mandatory and requested for baseline data collection.
- 6. Follow-up data collection period (e.g. months 6, 12, 18, 24, 30, 36) for patients who have started TDF before the entry of study will be anchored to their actual TDF initiation dates.

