6.1. Inclusion Criteria

Participants will be eligible to be included in this study only if all of the following criteria apply:

- 1. Male or female participants aged 12 years and above, at the time of signing the informed consent.
- 2. Participants who are diagnosed with CHB and meet the criterion of antiviral treatment for HBV infection judged by certified physicians.
- 3. Participants who newly initiate TDF ((only including brand TDF, Viread, and generic TDF, Beixin and Naxinde, which passed China generic quality consistency evaluation by Apr. 1 2018) monotherapy or combination therapy for the treatment of CHB by the judge of investigators at the study entry.
- 4. Participants who have already started TDF at the entry of study and will continue to be treated TDF (including brand TDF, Viread, and generic TDF, Beixin and Naxinde which passed China generic quality consistency evaluation by Apr. 01 2018) with essential medical information record and lab test reports available at the initiation of TDF treatment and follow-up visit.

Essential medical information record and lab test reports:

• *At the initiation of TDF treatment:*

- i. TDF treatment detail: TDF dose, brand name, start date;
- ii. Lab test (within +/-4 weeks of TDF treatment initiation): HBV DNA quantification (using high sensitive real-time PCR assays for HBV DNA quantification with lower limit of detection of 20IU/ml), ALT and/or AST, Serum creatinine and Serum phosphate, HBsAg/Anti-HBs and HBeAg/Anti-HBe
- iii. Medical information: CHB diagnosis and treatment history, co-morbidity, concomitant treatment
- The following visits under TDF treatment prior to entry of the study (At least once following visit record if TDF treatment >6 months):
 - i. Lab test: HBV DNA quantification (using high sensitive real-time PCR assays for HBV DNA quantification with lower limit of detection of 20IU/ml), Serum creatinine and Serum phosphate
 - ii. Medical information: co-morbidity, concomitant treatment, TDF treatment information

The proportion of patients who have already started TDF at the study entry will be monitored closely during study recruitment and will be kept less than 10% of the total study population.

- 5. Participants who are able to perform normal activities and seek regular medical care, e.g., willing to regularly perform lab test to monitor the treatment response.

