7.3. Follow Up Data Collection

Study participants will be followed up for 3 years or until they withdraw from the study. Follow-up information will be collected at 6-month intervals:

- Regular tests
 - o HBV serology
 - o HBV DNA
 - o Serum creatinine and eGFR [MDRD equation]
 - Serum phosphate
 - Alanine transaminase (ALT) and aspartate transaminase (AST)
- Other tests and procedures
 - o AFP
 - o Hepatic ultrasound
 - Genotype
 - o Bone mineral density

- Liver biopsy
- o Transient elastography (fibrotouch or fibroscan)
- Hepatic ultrasound /computed tomography (CT) /magnetic resonance imaging (MRI)
- Updated CHB treatment details, e.g. any change to regimen or dosage and reason for change
- Comorbidity and concomitant medication review
- Spontaneous AEs if available
- For treatment adherence, it will be evaluated by the treating physician according to the patients' care seeking care, e.g. whether take the medication as prescribed, have you ever discontinued your medications and for how long?
- For participants who discontinue TDF prematurely, duration of treatment and reasons for TDF discontinuation will be recorded, e.g. SAEs, non-SAEs, and insufficient effectiveness.

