7.4. Adverse Events and Pregnancy Events Data Collection

As this study takes a naturalistic design and minimizes the level of interventions, only spontaneous AEs will be collected, i.e. all serious and non-serious adverse events (AEs) and pregnancy exposures related to any GSK product (e.g., Viread) will be collected and reported as described in the study-specific pharmacovigilance plan (sPVP). Our special interest is the renal and bone toxicity related to TDF. In routine clinical practice, collecting and reporting spontaneous AEs including pregnancy exposure is the obligation of physicians. Such events will be evaluated and reported by investigators completing the Spontaneous AE Reporting Form for HCPs, Pregnancy Initial Notification Form for HCPs and Pregnancy Outcome Form for HCPs. The study SAP will oversee the spontaneous AE reports to be forwarded by CRO to local safety team who will report to GSK central safety department.

See study Pharmacovigilance Plan (sPVP) for details. sPVP will include the following elements to ensure a comprehensive approach to safety event collection and reporting:

- Supplier pharmacovigilance training
- Investigator and site staff pharmacovigilance training
- Safety-specific roles
- AEs / SAEs and pregnancy exposures collection and reporting processes
- AEs / SAEs and pregnancy exposures collection forms
- Frequency of data review
- Reporting process and timelines

- Interim reports
- Study-specific PVP monitoring process
- Provision of final study report

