9.3.4.3. Patient Treatment Adherence

The duration of patients on TDF treatment and the primary reason of discontinuation will be summarized using descriptive statistics as appropriate. The difference between CHB patients who continued TDF and those who discontinued will be explored in terms of socio-demographic and clinical characteristics (e.g. baseline HBV DNA level, HBeAg status, baseline alanine aminotransferase level, receipt or no-receipt of previous treatment with other NUCs, previous history of drug resistance, treatment-naïve or experienced, ADV or non-ADV, type of baseline co-morbidities).

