9.3.4.4. Spontaneous Adverse Events and Pregnancy Events

• Spontaneous AEs/SAEs will be summarized using descriptive statistics.

Adverse events will be assigned preferred terms and categorized into body systems according to the medical dictionary for regulatory activities (MedDRA) classification of the World Health Organisation terminology.

The proportion of subjects who experienced AEs will be calculated by dividing the number of subjects who experienced the AE during the treatment period by the number of subjects evaluable for safety analysis. Adverse events will be summarised by treatment group, and by body system and event within each body system. The following summaries of AEs will be provided:

All AEs.

All treatment related AEs.

All SAEs.

All treatment related SAEs.

All AEs leading to permanent discontinuation of study drug.

All AEs leading to permanent discontinuation from the study.

- Pregnancy events will be summarized using descriptive statistics. In addition, change from baseline of serum phosphate, serum creatinine, and creatinine clearance will also be summarized to evaluate the drug safety.
- The incidence of decompensated cirrhosis/liver disease and related complications, such as HCC, will be calculated for weeks of 48, 98 and 144, for the overall analysis population, and for certain sub-populations of interests, such as elderly and baseline Cirrhosis patients

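### AE and AE-discontinuation proportions count only spontaneous GSK-product-related reports over a denominator not limited by product, so AE-related stopping is likely undercounted and can disagree with the stopping-reason summary

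*Protocol*

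**What the plan says.** **Source of the AE data.** Note 4 to the Schedule of Activities (section 2) states that "only spontaneous AEs/SAEs and pregnancy exposure related to any GSK products will be reported and summarized". Section 7.4 repeats the restriction for collection and gives Viread as its example of a GSK product. Table 2 in section 4 words the matching exploratory objective as a summary by GSK product.

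**Who is enrolled.** Section 6.1 admits users of "brand TDF, Viread, and generic TDF, Beixin and Naxinde".

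**What is tabulated.** Section 9.3.4.4, under a heading on spontaneous events, lists all AEs, all SAEs, the treatment-related versions of both, and "All AEs leading to permanent discontinuation of study drug", with a parallel line for leaving the study. Each proportion is obtained by dividing "by the number of subjects evaluable for safety analysis". That population is not defined further; section 9.2 defines only the main analysis population, without a product limit.

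**Second record of stopping.** For participants who stop TDF early, section 7.3 says that "duration of treatment and reasons for TDF discontinuation will be recorded, e.g. SAEs, non-SAEs, and insufficient effectiveness". It sets no limit by brand. Section 8.2 also provides for collecting the reason, and its withdrawal rule names all three products. Section 9.3.4.3 says that "the primary reason of discontinuation will be summarized using descriptive statistics as appropriate". Section 9.3.5 adds the qualifier that the reason is obtained where possible.

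No section links the two sources or says which one defines AE-related discontinuation.

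**The concern.** The numerator of the AE tables is filtered by product and by causality, while the denominator is not. A patient on a generic can be counted below the line, but an event attributed only to that generic is outside the stated collection scope. An event in a Viread user that is not reported as related to a GSK product is outside it too. Despite their headings, the all-AE and all-SAE proportions are therefore not all-cause incidences.

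The discontinuation line matters most, because there the protocol holds a broader record: the section 7.3 reasons. Section 3.2 gives exploring TDF safety, in answer to clinicians' concerns, as the study's secondary purpose. A discontinuation proportion taken from the narrower source could give false reassurance, and the same report could show a different figure in the adherence section with nothing to explain the difference.

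**Working it through.** **1. The protocol's only AE figure.** Section 9.1.2 gives about 73% probability of seeing at least one AE at a true rate of 0.1%. With 2000 × 0.65 = 1300 completers, 1 − 0.999^1300 = 0.728, so it reproduces. (With all 2000 patients it would be 0.865.) The figure says nothing about discontinuation, but it treats every completer as able to yield an AE. If only GSK-product users can, the exponent becomes 1300 × (1 − g), where g is the generic share. The probability is then 69%, 60%, 48% or 32% for g = 10, 30, 50 or 70%.

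**2. Illustration of the discontinuation table.** The protocol gives no generic share, no AE-stop rate and no reporting completeness. All three are assumed here:
- True AE-stop rate 2% of 2000 = 40 patients, equal across brands.
- Generic share g from 0 to 70%. The generics are taken not to be GSK products, since section 7.4 names only Viread.
- s, the share of AE-related stops in GSK-product users that reach the table as related spontaneous reports, from 50 to 100%.

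Patients shown = 40 × (1 − g) × s; proportion = that number / 2000.

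| g | s = 1 | s = 0.75 | s = 0.5 |
|---|---|---|---|
| 0 | 40 (2.0%) | 30 (1.5%) | 20 (1.0%) |
| 0.1 | 36 (1.8%) | 27 (1.35%) | 18 (0.9%) |
| 0.3 | 28 (1.4%) | 21 (1.05%) | 14 (0.7%) |
| 0.5 | 20 (1.0%) | 15 (0.75%) | 10 (0.5%) |
| 0.7 | 12 (0.6%) | 9 (0.45%) | 6 (0.3%) |

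The share captured is (1 − g) × s, from 0.3 × 0.5 = 15% to 1 × 1 = 100%.

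**3. Effect of a matching denominator.** Dividing by GSK-product users gives 40(1 − g)s / [2000(1 − g)] = 2% × s. At g = 0.5 and s = 0.75 this is 15/1000 = 1.5% instead of 0.75%. The product part of the shortfall disappears; the reporting part remains.

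**4. The other source is not complete either.** Section 9.3.4.3 counts only the primary reason, and reasons can be missing. Let c be the share of AE-related stops that appear there as such; the count is 40 × c. With c = 0.8 (assumed) it is 32 patients. The AE table is lower whenever (1 − g) × s < c. At g = 0.3 and s = 0.75 it shows 21, below 32. At g = 0.1 and s = 1 it shows 36, above 32. So the order can reverse.

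**The case against.** The strongest reply has four parts.

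- **The two summaries do not measure the same thing.** One counts any AE leading to stopping; the other counts only the primary reason, recorded where possible. A reader might infer that the report will carry two conflicting rates and that the safety table will show the lower one. The documents do not support that certainty: with few generic users and full reporting the figures can agree, and step 4 shows that the order can reverse. Nor do they support saying that the stopping reason is held for every TDF user, since section 7.3 covers early stoppers only. This part stands.
- **The section 7.3 reasons cannot replace the AE table.** Section 9.3.4.4 calls for MedDRA coding and summaries by body system and event. Section 7.3 gives only broad reason categories as examples and does not say that an event term is recorded. This stands and limits the fix to a count.
- **The headings are clear in context.** The lines sit under a heading on spontaneous events, Table 2 limits the output by GSK product, and final titles belong to the analysis plan. This has some force for the titles, but not for the denominator, which section 9.3.4.4 itself states without a product limit.
- **The all-AE and treatment-related tables need not be duplicates.** A reader might infer that they must coincide. Collection covers any GSK product, so events related to another GSK product can separate them. This stands, although the protocol does not define treatment-related.

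These summaries are also exploratory in a descriptive study, so no primary or secondary result depends on them.

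**Conclusion.** The concern holds in a limited form. Followed as written, section 9.3.4.4 produces all-AE, all-SAE and AE-discontinuation proportions whose numerator leaves out events attributed only to a generic or to no GSK product, over a denominator with no such limit. AE-related stopping is likely to be undercounted, above all among generic users, and can disagree with section 9.3.4.3. The undercount relative to the true number of AE-related stops follows from the collection rule. The direction relative to the stopping-reason summary is likely but not certain.

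No size can be fixed from the protocol; the 15 to 100% capture range rests wholly on the assumed generic share and reporting completeness. The conclusion also assumes that the generics are not GSK products and that the undefined safety-evaluable population includes their users. The matter is worth correcting because the tolerability message depends on it and the change is small.

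**What to change.** In section 9.3.4.4:
- Report the number and proportion of patients who stopped TDF because of an SAE or a non-serious AE, from the section 7.3 reasons, for all TDF users and by product. Show the number of stoppers with no recorded reason.
- Reconcile that count with the spontaneous reports, and cross-refer to section 9.3.4.3 so that any difference is explained (primary reason versus any contributing AE, missing reasons, unreported events).
- Keep the table by body system and event for spontaneous reports only. Title it, and the all-AE and all-SAE tables, as reports related to a GSK product, with GSK-product users as the denominator.
- Define treatment-related as TDF-related.

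The count needs no data beyond what sections 7.2 (brand name) and 7.3 (reason) already provide for; the rest is table specification. The by-product split needs a rule for patients who change brand. The cost is that the AE-discontinuation rate may look less favourable, and that it carries no event terms for generic users.

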9.3.5. Other Analyses

Missing data is inevitable in this real-world study and can have an impact upon the interpretation of the data. In general, values for missing data will not be imputed unless otherwise specified. As this study takes a naturalistic approach, there will be no protocoldictated interventions or approaches to improve patient compliance besides what physicians do in practice. The study will use innovative electronic data capture approaches to increase the efficiency of data collection and reduce the effort on patients, physicians and sites, hopefully to reduce the chance of missing data.

The duration of patients on TDF, the reason for discontinuation if possible, and patients' adherence will be evaluated and recorded. Missing data issue will be explored in data analyses. For example, the reason and occurrence time of missing data will be summarized. It might be informative to know more the missing data and improve the adherence of treatment in the future.

When applicable, additional analyses may be conducted on primary, secondary, and exploratory objectives and research questions and will be described in RAP.

10. STUDY GOVERNANCE CONSIDERATIONS

In accordance with applicable regulations, GCP, and GSK procedures, GSK monitors (or delegators) will contact the site prior to the start of the study to review with the site staff the protocol, study requirements, and their responsibilities to satisfy regulatory, ethical, and GSK requirements.

GSK (or delegators) will monitor the study to ensure that the:

Data are authentic, accurate, and complete.

Safety and rights of subjects are being protected.

Study is conducted in accordance with the currently approved protocol and any other study agreements, GCP, and all applicable regulatory requirements.

Data will be collected using an innovative electronic approach, i.e. Smartphone APP, with the intention to reduce the data collection burden on patients, investigators, and sites and also improve data collection efficiency and quality in this study. All the data uploaded must be managed and retained in order to comply with all applicable law/regulatory requirements and GSK standard operating procedures.

11. INFORMED CONSENT PROCESS

Electronic informed consent form would be provided via the innovative digital approach in this study. Written informed consent must be obtained from each subject prior to participation in the study.

12. STUDY LIMITATIONS

This is a China-based multi-centre, prospective, longitudinal, non-interventional study conducted in a real-world setting in order to investigate long-term effectiveness and safety of TDF among Chinese CHB patients to guide clinical practice. The absence of comparison group is one of the major limitations to this study, which can be mitigated by a historical comparison leveraging previous trial data from literature or in-house alternatively. The mixing of the new initiator and on-treatment patients is another limitation, which may complicate the analysis due to varied treatment duration and inconsistent baseline information. Potential solutions include setting restriction on the inclusion criteria to the patients who have already started TDF prior to the entry of study in line with those of new initiators.

14. APPENDICES

Appendix 1: Abbreviations and Trademarks

Abbreviations

AE	Adverse event
ADV	Adefovir
ALT	Alanine aminotransferase
AFP	Alpha feto protein
BMD	Bone mineral density
CV	Cardiovascular
CHB	Chronic hepatitis B
CVR	Complete virological response
DM	Diabetes mellitus
DNA	Deoxyribonucleic acid
ETV	Entecavir
eGFR	Estimated glomerular filtration rate
HBeAg	Hepatitis B envelope antigen
HBsAg	Hepatitis B surface antigen
HBV	Hepatitis B virus
HCC	Hepatocellular carcinoma
HCP	Healthcare care professional
HIV	Human immunodeficiency virus
ICF	Informed consent form
IU/mL	International unit per millilitre
LAM	Lamivudine
LdT	Telbivudine
mL	Milliliter
mL/min/m ²	Milliliter per minute per meter square
MedDRA	Medical dictionary for regulatory activities
MDRD	Modification of diet in renal disease
NUC	Nucleos(t)ide analogues
PI	Principal investigator
RAP	Reporting and analysis plan
SAE	Serious adverse event
SD	Standard deviation
SOA	Schedule of activity
sPVP	study pharmacovigilance plan
TE	Transient elastography
TDF	Tenofovir disoproxil fumarate
%	Percentage

Trademark Information

Trademarks of the GlaxoSmithKline
group of companies

NONE

Trademarks not owned by the GlaxoSmithKline group of companies

Viread
Beixin
Naxinde
